## Document History

Version	Date	Author(s)	Description
0.1	18/DEC/2020	[name]	First draft version
0.2	17/MAR/2022	[name]	
Final draft
 
Besides minor editorial changes, the following sections were adapted:
 

• Section 4.2: Subgroups were further specified.

• Section 6.2: Derivation of time since implantation added.

• Section 7.3.3: Time to onset is calculated based on date of implantation.

• Section 7.4.2: Time since implantation added to other patient characteristics.

• Section 7.5: Clarification that device malfunctions will be identified among device deficiencies by a medical expert.

• Section 7.7: AEs of special interest and eye-related AEs will be identified by a medical expert. Analysis by eye was added.

• Section 7.8 Clarifications that external eye photography is not part of this SAP.

• Appendix: Tables for subgroup analysis added.

1.0	04/MAY/2022	[name]	Final version (Only minor editorial changes)

## List of Abbreviations and Key Terms

ADE	Adverse Device Effect
AE	Adverse Event
ATC	Anatomical Therapeutic Chemical classification system of the World Health Organization
BCVA	Best Corrected Visual Acuity
BMI	Body Mass Index
BMO-MRW	Bruch's Membrane Opening Minimum Rim Width
CIP	Clinical Investigation Plan
CYL	Cylindrical Component
D	Diopter
DCT	PASCAL Dynamic Contour Tonometry
eCRF	electronic Case Report Form
ETDRS	Early Treatment Diabetic Retinopathy Study
GAT	Goldmann Applanation Tonometry
IOP	Intraocular Pressure
logMAR	Logarithm of the minimum angle of resolution
max	Maximum
MedDRA	Medical Dictionary for Regulatory Activities
min	Minimum
miss	missing
MRSE	Manifest refraction spherical equivalent
N	Number of subjects
n	Number of non-missing observations
NEI VFQ-25	National Eye Institute Visual Function Questionnaire 25
OCT	Optical Coherence Tomography
PDF	Portable Document Format
POAG	Primary Open Angle Glaucoma
PT	Preferred Term
Q1	First Quartile
Q3	Third Quartile
RNFLT	Retinal Nerve Fiber Layer Thickness
RTF	Rich Text Format
SADE	Serious Adverse Device Effect
SAE	Serious Adverse Event
SAP	Statistical Analysis Plan
SAS®	Statistical Analysis System
SD	Standard Deviation
SE	Spherical Equivalent

SOC	System Organ Class
SPH	Spherical Component
WHO-CC	World Health Organisation Collaborating Centre for Drug Statistics Methodology

## 1. Introduction

This statistical analysis plan (SAP) contains a more technical and detailed elaboration of the principal features of the statistical analyses described in the Clinical Investigation Plan ARGOS-03, revision B, dated 11/JAN/2018. The purpose of the SAP is to serve as a guideline for statistical programming and creation of the analysis tables, figures and listings for the clinical investigation plan. The SAP is finalised and signed prior to hard lock of the database and start of the statistical analysis.

## 2. Study Design and Objectives

### 2.1 Study Design

This is a prospective, open-labeled, multicenter clinical follow-up investigation of the ARGOS-IO pressure sensor to evaluate the long-term safety and performance of the ARGOS-IO system in patients with primary open angle glaucoma (POAG).

The ARGOS-IO system was developed for the wireless, contactless measurement of the hydrostatic pressure of the aqueous humor (intraocular pressure, IOP) patients with diagnosed glaucoma, or elevated or instable IOP that places them at a risk of ocular damage and loss of visual acuity. It is intended to be implanted during cataract surgery, and to remain in place indefinitely. Because the sensors are implanted in the eye, the ARGOS-IO pressure sensor measures IOP directly, without interference from corneal properties or due to operator skill.

In the early feasibility ARGOS-01 study, six glaucoma patients (4 POAG and 2 Normal Pressure Glaucoma) at a single university eye clinic in Germany had an earlier version of the ARGOS-IO pressure sensors implanted in the ciliary sulcus concomitantly to cataract surgery. Promising concurrence was seen between IOP profiles obtained with ARGOS-IO, GAT and DCT over the 12 months follow-up period and the ARGOS-IO system was easily used by the patients in the home setting. However, after two fibrin reactions classified as procedure-related SAEs were observed, as were multiple adverse events possibly caused by the size and/or form of the implant, the sponsor stopped the study to investigate the cause.

As a result of these tests and the ARGOS-01 study, modifications were made to the form of the device and the implantation procedure to improve the device's safety profile. The ARGOS-02 study investigated the safety and performance of the ARGOS-IO system (second generation) in patients with primary open angle glaucoma. Over a one-year period, 22 patients undergoing phacoemulsification and IOL implantation for cataract received ARGOS-IO implants in an add-on procedure. Their eye condition and IOP were followed over the course of 12 months. The reported results indicate that the modifications to the sensor design implemented after the ARGOS-01 trial as well as the introduction of an injector device for the implantation of the ARGOS-IO pressure sensor

have led to a significant improvement of the safety and performance profile of the investigational device.

This trial is designed to obtain additional data on the long-term safety and performance of the ARGOS-IO system through the observation of patients previously implanted with the ARGOS-IO system as part of the ARGOS-01 and ARGOS-02 clinical trials. Up to five (5) patients of the ARGOS-01 and up to 21 patients of the ARGOS-02 study will take part in the study. All patients were implanted in their respective study with the ARGOS-IO implant in one eye only, which will be considered the study eye. All patients will be followed for 36 months.

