### 2.4.2 Primary Safety Objective

The safety objective of this trial is to evaluate the long-term safety and tolerability of the ARGOS-IO pressure sensor under consideration of incidence, nature, severity, and seriousness of observed medical device related adverse and serious adverse events. Safety has been defined as co-primary objective of this trial.

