### **4.2 Subgroups**

In order to investigate the impact of certain characteristics on performance, the primary variables will also be examined, provided that there are enough subjects in the respective subgroup, by the following variables:

- Size of ARGOS-IO implant (outer diameter of: 11.3 mm, 11.7 mm or 12.1 mm)
- Gender (male, female)
- Age groups ( $\leq 70$  years at Visit 01,  $> 70$  years at Visit 01)
- Educational level (A-Level, Intermediate, Primary, University, Vocational, Other)

A subgroup analysis for the respective subgroups will only be performed if at least two of the features contain five (5) or more patients.

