#### 8.2 Performance

- 8.2.1 Comparison of intraocular pressure measurements (IOP)
  - 8.2.1.1 IOP measurements with ARGOS-IO and comparators by visit
  - 8.2.1.2 Limits of agreement between IOP measurements with ARGOS-IO and comparators by visit
  - 8.2.1.3 Limits of agreement between IOP measurements with ARGOS-IO and comparators by subgroup and visit
- 8.2.2 Device malfunctions
  - 8.2.2.1 Summary of device malfunctions
  - 8.2.2.2 Summary of device malfunctions by subgroup
  - 8.2.2.3 Device malfunctions per 10 patient years
- 8.2.3 Glaucoma progression by visit
- 8.2.4 Change in glaucoma medication
  - 8.2.4.1 Summary of changes in glaucoma medication
  - 8.2.4.2 Changes in glaucoma medication per 10 patient years
- 8.2.5 Unscheduled visits due to self-measured increased IOP

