#### 8.3 Safety data

- 8.3.1 Adverse Events (AEs) and device related adverse events (ADEs)
  - 8.3.1.1 Overall summary of AEs
  - 8.3.1.2 Overall summary of ADEs
  - 8.3.1.3 Subjects with eye-related AEs and number of eye-related AEs by SOC and PT
  - 8.3.1.4 Subjects with eye-related ADEs and number of eye-related ADEs by SOC and PT
  - 8.3.1.5 Subjects with eye-related AEs by worst severity, SOC and PT
  - 8.3.1.6 Subjects with eye-related ADEs by worst severity, SOC and PT
  - 8.3.1.7 Subjects with eye-related AEs by seriousness, SOC and PT

- 8.3.1.8 Subjects with eye-related ADEs by seriousness, SOC and PT
- 8.3.1.9 Eye related ADEs per 10 patient years
- 8.3.2 Deaths and other serious / significant adverse events
- 8.3.2.1 Serious AEs, listing of subjects
- 8.3.2.2 Deaths, listing of all serious AEs of subjects who died
- 8.3.2.3 AEs leading to discontinuation, listing of subjects

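### The SAP leaves open whether co-primary safety is examined by implant size, and it drops the ARGOS-01/ARGOS-02 split without recording the change

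*SAP*

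**What the plan says.** SAP 2.1 (and CIP 4.2) says that ARGOS-01 was stopped after two fibrin reactions classed as serious and "multiple adverse events possibly caused by the size and/or form of the implant". The implant was then redesigned for ARGOS-02. SAP 2.4.2 states: "Safety has been defined as co-primary objective of this trial".

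On subgroups, SAP 4.2 opens: "In order to investigate the impact of certain characteristics on performance, the primary variables will also be examined". One subgroup is "Size of ARGOS-IO implant (outer diameter of: 11.3 mm, 11.7 mm or 12.1 mm"; the others are gender, age group and educational level. A subgroup analysis "will only be performed if at least two of the features contain five (5) or more patients".

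The appendix names two subgroup tables, both under Performance: "Limits of agreement between IOP measurements with ARGOS-IO and comparators by subgroup and visit" (8.2.1.3) and "Summary of device malfunctions by subgroup" (8.2.2.2). The safety tables, for example "Subjects with eye-related ADEs and number of eye-related ADEs by SOC and PT" (8.3.1.4), carry no subgroup. SAP 7.7 splits all eye-related AEs by study eye and fellow eye only.

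CIP 7.6 uses nearly the same opening sentence, again with performance as the aim. Its list begins with two entries that SAP 4.2 lacks: ARGOS-01 patients and ARGOS-02 patients.

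**The concern.** Implant geometry, in the broad sense of size and form, is what the sponsor suspected behind the ARGOS-01 events, and it is what the redesign changed. A reader of the long-term safety result will want to know whether the rate applies to both implant generations and to all three diameters of the current one. As planned, the main safety figure is a single rate over all enrolled patients.

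The generation split matters more. CIP 4.2 reports different adverse event frequencies for the two designs, for example pigment dispersion in 5 of 6 ARGOS-01 patients and 8 of 22 ARGOS-02 patients. Those figures come from the original trials and do not predict late events, but they are a reason not to pool the generations without also showing them apart. If the tables are settled only after the events are known, the choice of split will look driven by the data.

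**Working it through.** **The plan's own figure.** Maximum enrolment is 5 (ARGOS-01) + 21 (ARGOS-02) = 26, as SAP 2.9 states. There is no power calculation to reproduce.

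**Text side by side.**

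| Place | Safety by subgroup? |
|---|---|
| SAP 4.2, object | Primary variables; SAP 6.5 is headed as primary safety variables, so they can be included |
| SAP 4.2, aim | Performance only |
| SAP 7.7 | By eye only; no implant subgroup |
| Appendix 8.2 | Two subgroup tables, both performance |
| Appendix 8.3.1.1 to 8.3.2.3 | No subgroup table |
| CIP 7.6 | Primary endpoints by ARGOS-01/ARGOS-02, among others; aim again performance |
| SAP Section 8 | Records only the change to the agreement analysis |

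SAP 2.11 asks that changes to the analyses planned in the CIP be justified and documented in the SAP text. The document history describes the version 0.2 edit of 4.2 as a further specification of subgroups, not a removal. One caution: SAP Section 1 cites CIP revision B, and the CIP available here is revision C. The omission is established against revision C.

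**What is mixed.** CIP 6.1.1 gives ARGOS-01 implants as 11.3 mm across and 0.9 mm thick, and ARGOS-02 implants as 11.3, 11.7 or 12.1 mm across and 0.5 mm thick, with haptics added. The 11.3 mm level in SAP 4.2 therefore contains both generations.

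**The five-patient rule.** At most five ARGOS-01 patients can enrol. A generation split under the SAP 4.2 rule would be lost if even one of them declined.

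**Arithmetic (illustration).** Assume every patient reaches Day 1080, so patient years T = n × 1080/365.25 = n × 2.957. This gives 14.8 (n = 5), 20.7 (n = 7), 62.1 (n = 21) and 76.9 (n = 26). The rate is 10k/T. The exact Poisson limits are 10 × χ²(0.025; 2k)/(2T) and 10 × χ²(0.975; 2k+2)/(2T). The count limits are 0 to 3.689 for k = 0, 0.619 to 8.767 for k = 3, and 2.202 to 13.059 for k = 6.

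| Assumed events | Group | Rate per 10 patient years (95% CI) |
|---|---|---|
| 0 | ARGOS-01, n = 5 | 0 (0 to 2.50) |
| 0 | ARGOS-02, n = 21 | 0 (0 to 0.59) |
| 0 | All, n = 26 | 0 (0 to 0.48) |
| 3 | ARGOS-01, n = 5 | 2.03 (0.42 to 5.93) |
| 3 | ARGOS-02, n = 21 | 0.48 (0.10 to 1.41) |
| 3 + 3 = 6 | All, n = 26 | 0.78 (0.29 to 1.70) |

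For diameter within the second generation, assume 7 patients per size. Six events all in one size give 2.90 (1.06 to 6.31) there and 0 (0 to 1.78) in each other size. The like-for-like pooled rate over those 21 patients is 6/62.1 × 10 = 0.97 (0.35 to 2.10). Dividing the same six events by all 26 patients gives 0.78, but that assumes the five ARGOS-01 patients are event-free.

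**The case against.** The strongest reply is that SAP 4.2 already covers safety. Its object is the primary variables, and SAP 6.5 lists primary safety variables. Silence in 7.7 proves little, because SAP 7.5 is equally silent on subgroups and yet both of its outcomes have subgroup tables. The appendix says its table list is not mandatory and may be adapted. The performance wording comes from CIP 7.6, so the SAP did not narrow it. An adverse event listing by patient (12.2.7.1) is also planned.

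Much of this stands. A reader might infer that the SAP excludes safety from the size subgroup; the text does not go that far. But the stated aim points the other way. According to the document history, the subgroup tables were added to the appendix in version 0.2, and they appear only under Performance. Adaptation of the list must follow the analyses described, and a programmer cannot tell from 4.2 and 7.7 whether a safety table is one of them.

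A second reply concerns the premise. A reader might infer that the documents suspect outer diameter of causing harm. They do not. The remark names size and/or form and concerns an implant made in one diameter, 11.3 mm, which ARGOS-02 kept. CIP 4.2 follows the problem to radial force and curvature, and the redesign changed thickness and added haptics. The three diameters were introduced to fit the individual eye, so diameter is tied to anatomy and a difference between sizes would not be causal. This is correct, and it is why generation should be the first split and diameter only the second.

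None of this answers the unrecorded loss of the ARGOS-01/ARGOS-02 split.

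**Conclusion.** The point holds as an internal inconsistency combined with an undocumented departure from CIP 7.6. Two subgroup tables are listed, both for performance. No safety table is listed by implant diameter or by generation, and the wording of 4.2 supports either reading. The omission of the generation split is clear against CIP revision C.

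Its numerical size cannot be established, because the documents give neither patients per diameter nor event counts. With no events at all, the pooled upper limit of 0.48 per 10 patient years would sit beside 2.50 for first-generation implants alone, so the pooled figure says little about that group. With three events in each generation, the separate rates differ by a factor of 21/5 = 4.2, but their intervals overlap.

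The six-events-in-one-size pattern is an extreme case. It should not be read as evidence that a cluster exists or that a pooled rate would be taken as reassurance for every size. These figures assume full enrolment and follow-up to Day 1080. The pooled rate remains a valid descriptive summary; what is missing is the breakdown needed to interpret it.

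**What to change.** 1. In SAP 4.2, change the aim to cover performance and safety, and restore the ARGOS-01/ARGOS-02 split. If its removal was intended, justify it in Section 8.
2. In SAP 7.7 and tables 8.3.1.4 and 8.3.1.9, add counts and percentages of patients, and rates per 10 patient years with exact intervals, for device-related AEs, device-related SAEs and AEs of special interest in the study eye.
3. Show these first by implant generation, descriptively, even if fewer than five ARGOS-01 patients enrol. Then show them by diameter within second-generation implants, under the existing five-patient rule.
4. State that the splits are descriptive and that diameter was chosen by eye fit.

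The cost is a few sentences and a small number of tables. Diameter is already needed for the performance subgroups, and generation follows from the trial in which the patient was implanted. The drawback is small groups with wide intervals, which cannot support a causal comparison.

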## 2.2 Treatments

Only patients that participated in the ARGOS-01 or ARGOS-02 study may be enrolled in this study. All potential patients have therefore already been implanted with the ARGOS-IO implant as part of their previous study participation. No additional treatment is envisaged for the ARGOS-03 trial.

## 2.3 Trial Schedule

All enrolled patients are seen according to the following schedule.

Visit 01	Day 0
Visit 02	Day 180 ( $\pm$ 3 weeks)
Visit 03	Day 360 ( $\pm$ 3 weeks)
Visit 04	Day 540 ( $\pm$ 3 weeks)
Visit 05	Day 720 ( $\pm$ 3 weeks)
Visit 06	Day 900 ( $\pm$ 3 weeks)
Visit 07	Day 1080 ( $\pm$ 3 weeks)

Table 1, shown below, lists all assessments to be done at the respective study visits for patient or study eye.

**Table 1: Visit Schedule**

Visits	V01	V02	V03	V04	V05	V06	V07
Indicative Days (D)	D0	D180 +/- 3 wks	D360 +/- 3wks	D540 +/- 3wks	D720 +/- 3wks	D900 +/- 3wks	D1080 +/- 3wks
General							
Informed Consent	X						
Handout of the patient diary	X						
Demographics	X						
Past and current significant medical history	X						
Comparative measurements	X						
Check of the functionality of the Mesograph and Multiline Connector	X						
Confirmation of the correct function of the ARGOS-IO sensor	X						
Visual acuity (EDTRS)  (both eyes)	X	X	X	X	X	X	X
Perimetry (both eyes)	X	X	X	X	X	X	X
Concomitant medications	X	X	X	X	X	X	X
Eye related AEs/ADE/SAE/SADE	X	X	X	X	X	X	X
NEI VFQ-25	X		X		X		X
Device deficiency		X	X	X	X	X	X
Check patient diary for completeness		X	X	X	X	X	X
Anterior Segment (both eyes)							
External eye photography (Slit lamp)	X	X	X	X	X	X	X
Slit-lamp biomicroscopy	X	X	X	X	X	X	X
Optical coherence tomography 	X	X	X	X	X	X	X
Corneal endothelial cell density	X	X	X	X	X	X	X
Gonioscopy	X	X	X	X	X	X	X
Posterior Segment (both eyes)							
Funduscopy	X	X	X	X	X	X	X
Optical coherence tomography 	X	X	X	X	X	X	X
Fundus photography 	X		X		X		X
IOP measurement							
Goldmann Applanation (both eyes)	X	X	X	X	X	X	X
Pascal DCT (both eyes)	X	X	X	X	X	X	X
ARGOS-IO clinic	X	X	X	X	X	X	X
ARGOS-IO home 	X	X	X	X	X	X	X

The best corrected visual acuity will be determined after objective and subjective determination of refraction with the EDTRS chart.

Anterior segment OCT is performed to assess the central cornea thickness and to evaluate effects on change in chamber angle after implantation.

Posterior segment OCT is used to assess macular structures and the peripapillary nerve fibre layer thickness (RNFLT) and (if possible) BMO-MRW

The fundus should be photographed in order to document potential changes to the optic nerve (cup/disc ration) and nerve fibre layer (red-free illumination).

IOP-measurements will be performed in series of 2 GAT measurement (with difference more than 2mmHg, a third GAT-measurement is required) and 3 directly consecutive measurements with the ARGOS-IO system followed by 2 Pascal tonometry (with difference more than 2mmHg, a third DCT-measurement is required) and 3 directly consecutive measurements with the ARGOS-IO system.

For the non-study eye, only GAT and DCT measurements will be performed as described above.

All measurements should be performed directly one after another.

Measurements at home shall be taken at least 4 times per day (morning, noon, afternoon, evening). Once a month, an “IOP day” will be scheduled with measurements every hour and additionally one-hour pre and post drug administration. The activities on that day will be documented in a patient dairy.

Optional: Quarterly additional night measurements on one of the “IOP days”. Patients will be supplied therefore with the MESOGRAPH antenna patch which will do the measurements automatically.

## 2.4 Study Objectives

The objective of this clinical study is to verify the long-term safety and performance of the ARGOS-IO intraocular pressure sensor system in subjects with POAG. The measurements of intraocular pressure through the pressure sensor shall be compared with Goldmann Applanation Tonometry (GAT), which is generally accepted as the clinical gold standard, and the Pascal Dynamic Contour Tonometer (DCT).

### 2.4.1 Primary Performance Objective

The primary performance objective of this trial is to evaluate the performance of the ARGOS-IO system compared to Goldmann Applanation Tonometry (GAT) and Pascal Dynamic Contour tonometry (DCT) by means of their limits of agreement.

Additionally, incidences and nature of observed device malfunctions of the ARGOS-IO system will be evaluated.

### 2.4.2 Primary Safety Objective

The safety objective of this trial is to evaluate the long-term safety and tolerability of the ARGOS-IO pressure sensor under consideration of incidence, nature, severity, and seriousness of observed medical device related adverse and serious adverse events. Safety has been defined as co-primary objective of this trial.

### 2.4.3 Secondary Objectives

The following secondary objective have been defined for this trial:

- Evaluation of patient compliance in intraocular pressure (IOP) self-monitoring
  - Daily self-measurements with the ARGOS-IO sensor should be done at least 4 times daily (morning, noon, afternoon, evening)

- Evaluation of the impact of IOP self-monitoring on glaucoma progression
  - Parameters to evaluate the glaucoma progression are visual field, cup/disc ratio, OCT of the optic nerve and the IOP
- Evaluation of incidences in glaucoma medication change
- Evaluation of the number of unscheduled visits due to self-measured increased IOP
  - The patients decide to come for a visit by their own due to any reason. This will be documented

## 2.5 Study Hypothesis

All analyses will be performed in an exploratory and descriptive manner. Therefore, no study hypothesis was defined for this trial.

## 2.6 Handling of Screen Failures and Drop-outs

All patients having participated in the ARGOS-01 or ARGOS-02 are eligible for this study. Any of these patients not willing to participate in this study will not be replaced. Any patient willing to participate in this study will be considered enrolled.

If an enrolled patient discontinues the study prematurely or is lost to follow-up, the patient is considered a drop-out. Patients who drop out before completion of the study at Visit 07 (day 1080) will not be replaced.

## 2.7 Randomization and Stratification

No randomisation or stratification is applied.

## 2.8 Blinding

No blinding procedures are applied.

## 2.9 Sample Size Calculation

Given the exploratory nature of this study, the sample size is not driven by the need for a formal statistical hypothesis test with a certain degree of power and no formal sample size calculation had been performed. Instead, this study is driven by the desire to obtain a clinically meaningful amount of data to evaluate the long-term safety and performance of the ARGOS-IO system in patients who have already been implanted with the study device. Therefore, the maximum sample size is 26. This maximum sample size is composed of maximal 5 available subjects from the ARGOS-01 study and

maximal 21 available subjects from the ARGOS-02 study. It is envisaged to enroll all of these subjects.

The minimal sample size for this study is at the Sponsor's discretion. This is considered to be appropriate since no experimental treatments are planned and all assessments with exception of IOP measurement using the ARGOS-IO device are established standard methods.

